### **Valid disease assessment**

A valid post-baseline disease assessment is one for which the “time point response” is not “NE” (not evaluable) as per IMWG (see [Appendix D](#)). If the date of assessment is missing, the disease assessment is not valid.

Date of last valid disease assessment without evidence of PD: For a given time point not showing disease progression, if several exams are performed at different dates, the date of the last valid disease assessment is the date of latest exam.

### **Non-evaluable cases**

Missing exams: if one protocol planned examination is missing for a given disease assessment, the overall response should generally be NE or response assessment should be downgraded to the lowest IMWG response criteria unless there is clear evidence of progression (independently of the missing examination). Specific rules applying to missing serum or urine M-protein are described in the IRC charter.

For the primary analysis of PFS, progression or death occurring after a disease evaluation with an overall time point response(s) equal to NE will be considered as an event in the analysis. Such progression or death will be censored in the PFS sensitivity analysis #5 if occurring more than 8 weeks after the last valid tumor assessment without progression.

### **2.1.3.2 Secondary efficacy endpoint(s)**

#### **2.1.3.2.1 Key secondary efficacy endpoints**

Two key secondary efficacy endpoints are considered:

- Overall Response Rate (ORR), as per IMWG criteria.
- Overall Survival (OS).

Best Overall Response (BOR) and Clinical Benefit Rate will also be derived.

#### **Overall response rate (ORR)**

ORR is defined as the proportion of patients with stringent complete response (sCR), complete response (CR), very good partial response (VGPR), and partial response (PR), as BOR, assessed by the IRC using the IMWG response criteria.

For patients with non-measurable M-Protein on Cycle 1 Day 1 the only 3 possible overall responses are: CR, non-PD or PD (see [Appendix D](#)).

An additional analysis of ORR using investigator assessment of response will also be performed.

#### **Overall survival (OS)**

OS is defined as the time from the date of randomization to date of death from any cause. If death is not observed before the analysis data cut-off date, OS will be censored at the last date that the patient is known to be alive or at the cut-off date, whichever comes first.

#### **Best Overall Response (BOR)**

BOR is defined as the best sequential response, using the IRC's assessment of response, from the start of treatment until disease progression (provided that the progression is subsequently confirmed in case of progression requiring confirmation), death, initiation of further anti-myeloma treatment, or cutoff date, whichever occurs first. The ordering of evaluations from best to worse is: stringent complete response (sCR), complete response (CR), very good partial response (VGPR), partial response (PR), minimal response (MR), stable disease (SD), progressive disease (PD), not evaluable (NE). In addition, for patients with VGPR as BOR, the following subcategories will be assessed by the IRC: biochemical CR and near CR.

A confirmation assessment for disease response is required in this study (either MR or better, or PD, except PD diagnosed on radiological assessment).

BOR according to investigator assessment of response will also be provided.

#### **Clinical Benefit Rate (CBR)**

CBR is defined as the proportion of patients achieving a MR or better as BOR.

### **VGPR Rate**

VGPR rate is defined as the proportion of patients achieving a VGPR or better as BOR.

#### *2.1.3.2.2 Other secondary efficacy endpoints*

Other secondary efficacy endpoints will be evaluated as follows:

### **Time to Progression (TTP)**

TTP is defined as the time from the date of randomization to the date of first documentation of progressive disease (as determined by IRC). The same definition of progression and same censoring rules as for the PFS primary endpoint will be used.

### **PFS in the high risk cytogenetic population**

It is defined as PFS ([Section 2.1.3.1](#)) in the subgroup of patients carrying del(17p) and/or t(4;14) and/or t(14;16) assessed by FISH.

### **Duration of response (DOR)**

DOR is defined as the time from the date of the first IRC determined response that is subsequently confirmed to the date of first documented progression as assessed by IRC or death, whichever happens first. In the absence of the confirmation of subsequent disease progression or death before the analysis cut-off date, the DOR will be censored at the date of the last valid disease assessment not showing disease progression performed prior to initiation of a further anti-myeloma treatment or the analysis cut-off date, whichever is earlier.

Duration of response is determined only for patients who have achieved a response of PR or better (subsequently confirmed).

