--	--

[figure not shown]
	
known to be alive or the cut-off date, whichever is first. The final OS analysis (based on 220 deaths) is expected to be performed approximately 33 months after the final PFS analysis cut-off date (ie, 51 months after first patient in).
 
The analysis of DOR will be similar to that described for PFS. The same censoring rules as PFS will be used.
 
Analysis of PRO endpoints:
 
• Disease-specific HRQL (EORTC QLQ-C30) will be assessed via a comparison of C30 health-related quality-of-life change scores from baseline to EOT and 60 days after last study treatment administration between treatment arms. In addition responder analyses will be conducted: 1. for those who improve and 2 for those who deteriorate utilizing the clinical important differences (CID) defined in Appendix H for all C30 HRQL summary and subscale scores for both treatment arms.• Disease- and treatment-related symptoms (EORTC QLQ-C30 and MY20) will be assessed via a comparison of change scores in C30 (individual symptom change scores) and MY20 (disease- and treatment-related summary scores) from baseline to EOT and 60 days after last study treatment administration between treatment arms. In addition responder analyses will be conducted 1 for those who improve and 2 for those who deteriorate utilizing the CIDs defined in Appendix H for all individual symptom scores (C30) and disease- and treatment-related summary scores (MY20) for both treatment arms (Appendix I).• Health state utility (EQ-5D-5L) will be assessed via a comparison of health state utility change scores from baseline to EOT and 60 days after last study treatment administration between treatment arms. In addition responder analyses will be conducted 1 for those who improve and 2 for those who deteriorate utilizing the CIDs defined in Appendix J for health state utility scores for both treatment arms.• Health status (EQ-5D-5L Visual Analogue Scale) will be assessed via a comparison of EQ-5D-5L health status change scores from baseline to EOT and 60 days after last study treatment administration between treatment arms. In addition responder analyses will be conducted 1 for those who improve and 2 for those who deteriorate utilizing the CIDs defined in Appendix J for health status VAS scores for both treatment arms.• Clinically meaningful improvements for each PRO are defined (based on CIDs) in Appendix H, Appendix I and Appendix J. 
Analysis of the safety endpoints:
 
Number (%) of patients experiencing TEAEs by primary system organ class and preferred term will be summarized by CTCAE grade (all grades and \geq Grade 3) for the safety population. The same summaries will be prepared for drug-related TEAEs, TEAEs leading to treatment discontinuation, TEAEs leading to dose modification, serious TEAEs and TEAEs with fatal outcome. For patients with multiple occurrences of the same AE within the on-treatment period, the worst grade will be used.

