11.4.2 Analyses of efficacy endpoints

11.4.2.1 Analysis of primary efficacy endpoint(s)

The primary analysis of PFS will be based on the following censoring rules: If progression and death are not observed before the analysis cut-off date, PFS will be censored at the earliest of the date of the last valid disease assessment not showing disease progression performed prior to initiation of a further anti myeloma treatment (if any) or the analysis cut-off date, whichever comes first.

Primary analysis will consist of PFS comparison between IPd group versus Pd group through a 1-sided log-rank test procedure stratified by stratification factors as entered in the IRT (ie, age and number of previous lines of therapy).

This analysis will be performed on the ITT population.

Response will be determined according to IMWG criteria (1). The date of disease progression is the date of the first documented (and further confirmed) progression according to IMWG criteria as assessed by IRC. For patients without measurable M protein on Cycle 1 D1 efficacy laboratory results, progression and date of progression will be assessed by IRC according to criteria defined in [Appendix D](#).

A patient without an event (death or disease progression) and without any valid post-baseline disease assessments will be censored at the day of randomization (Day 1).

The cut-off date for the analysis of PFS is expected to be the date when the 162nd event (first occurrence of either disease progression or death due to any cause) has been observed.

The estimates of the hazard ratio and corresponding 95% confidence interval will be provided using a Cox proportional hazard model stratified by the same stratification factors as those used for the log-rank test described above. The survival curves will be estimated using Kaplan-Meier estimates. At the time of PFS final analysis, critical value for the logrank test on PFS hazard rate would be 0.734.

Sensitivity analyses of PFS will be performed (eg, different censoring rules and PFS assessed by the Investigator).

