### **2.1.3 Efficacy endpoints**

#### **2.1.3.1 Primary efficacy endpoint(s)**

The primary endpoint is Progression Free Survival (PFS) defined as the time from the date of randomization to the first documented date of progressive disease or death due to any cause before the analysis cut-off, whichever comes first. Patients without disease progression or death before the analysis cut-off or the date of initiation of further anti-myeloma treatment, will be censored at the earliest of the date of the last valid disease assessment not showing disease progression performed prior to initiation of a further anti-myeloma treatment (if any) or the analysis cut-off date, whichever comes first.

An independent response committee (IRC) blinded to the randomization arm and to the patient characteristics will evaluate disease assessments at each time point and determine disease response including progression status per IMWG criteria (1) ([Appendix D](#)). The full details regarding the determination of the progressive disease are provided in protocol and the IRC charter. The date of disease progression as determined by the IRC will be used for primary PFS analysis.

A patient without PFS event (death or disease progression) and without any valid post-baseline disease assessments will be censored at the day of randomization (Day 1).

Additional details regarding the definition of PFS and handling of events and censoring are given in [Appendix E](#).

Other censoring rules used for sensitivity analyses are provided in [Section 2.4.4.1.1](#).

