### **Determination of the PFS status for the primary analysis**

The following rules will be applied to determine if a patient has an event or is censored for the PFS primary analysis:

- For a patient who did not die and did not reach progressive disease before the cut-off date, the patient is censored and the censoring date is determined as follows:
  - If the patient received any further anti-myeloma treatment, then the censoring date is the date of last valid disease assessment without evidence of PD before the start of further anti-myeloma treatment, or the cut-off date, whichever comes first,
  - If the patient did not take any further anti-myeloma treatment then the censoring date is the date of last valid disease assessment without evidence of PD or the cut-off date, whichever comes first.
- For a patient who died or reached progressive disease before the cut-off date:
  - If the patient received any further anti-myeloma treatment before death or progression is documented, then the censoring date is the date of last valid disease assessment without evidence of PD before the start of further anti-myeloma treatment,
  - If the patient reached the PFS endpoint before initiation of further anti-myeloma treatment, the date of the event will be the date of progressive disease or death if no progression occurred.

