## **TTP, DOR, TTIR and TTBR**

These time-to-event endpoints will be analyzed using Kaplan-Meier methods.

Similarly to the primary analysis of PFS, if progression and death (excluding for TTP: only progression) are not observed before the analysis data cut-off date, TTP and DOR will be censored at the date of the last valid disease assessment not showing disease progression performed prior to initiation of further anti-myeloma treatment (if any) or the data cut-off date, whichever comes first.

If no response (PR or better) is observed before the analysis cut-off date, TT1R and TTBR will be censored at the date of the last valid disease assessment before disease progression or death, the date of the last valid disease assessment before initiation of a further anti-myeloma treatment (if any) or the analysis cut-off date, whichever comes first.

Analysis of the pre-specified secondary endpoints will be descriptive only. Any testing procedure carried out on these endpoints will be considered as exploratory.

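### The SAP's DOR and TTP text omits the primary PFS rule that events after new anti-myeloma therapy do not count, so read literally its censoring depends on the later outcome

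*SAP*

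**What the plan says.** **Primary PFS in the SAP.** The definition in Section 2.1.3.1 names two limits, the cut-off and the start of new therapy: "Patients without disease progression or death before the analysis cut-off or the date of initiation of further anti-myeloma treatment, will be censored". The rules for PFS status then deal with patients who did progress or die before cut-off: "If the patient received any further anti-myeloma treatment before death or progression is documented, then the censoring date is" the last valid assessment without progression before that treatment. Table 13 in Appendix E agrees. An event after new therapy is therefore not a PFS event.

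**DOR and TTP in the SAP.** The DOR definition in Section 2.1.3.2.2 names only the cut-off: "In the absence of the confirmation of subsequent disease progression or death before the analysis cut-off date, the DOR will be censored" at the last valid assessment before new therapy or at cut-off, whichever is earlier. Section 2.4.4.2 has the same structure for both endpoints: if the events "are not observed before the analysis data cut-off date, TTP and DOR will be censored at the date of the last valid disease assessment" before new therapy. The TTP definition in Section 2.1.3.2.2, however, says "The same definition of progression and same censoring rules as for the PFS primary endpoint will be used".

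**Protocol.** The synopsis says of DOR: "The same censoring rules as PFS will be used". The protocol's own PFS rule (synopsis and Section 11.4.2.1) names only the cut-off: "If progression and death are not observed before the analysis cut-off date, PFS will be censored at the earliest of the date". Section 11.4.2.2.2 uses that form for TTP, DOR and PFS in the high-risk cytogenetic population.

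**The concern.** The DOR and TTP text takes the censoring date from the PFS rule but not the condition that triggers censoring. Taken at its word, it applies one rule to patients who later have an event and another to those who do not. Time after new therapy is kept for the former and discarded for the latter. Kaplan-Meier estimation assumes that censoring is unrelated to the outcome to come, and this rule breaks that assumption.

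The literal rule is also not a recognisable alternative. It is neither the primary PFS rule nor the rule that ignores new therapy (PFS sensitivity analysis #1). It fits poorly with best overall response, which is assessed only until further anti-myeloma treatment starts.

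At stake are the descriptive DOR and TTP estimates, and whether the same patient has the same status in PFS and DOR.

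**Working it through.** **1. The three rules for one patient.** Take a responder who starts new therapy at month 6 without progression.

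| Later course | SAP primary PFS rule | DOR text read literally | New therapy ignored |
|---|---|---|---|
| Progression at month 9 | censored near month 6 | event at month 9 | event at month 9 |
| No event by cut-off | censored near month 6 | censored near month 6 | censored at last valid assessment up to cut-off |

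The literal rule follows the right-hand column in the first row and the PFS column in the second.

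**2. Such events are seen.** The protocol continues disease assessment until progression even when new therapy has begun (synopsis assessment schedule; Section 1.2, footnote ff; Section 10.1.5.2). Sensitivity analysis #1 relies on IRC events after new therapy.

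**3. Direction, as a constant-hazard sketch.** After new therapy, let d be the number of events, T_e the follow-up of patients who have one and T_f the follow-up of those who do not. The post-therapy hazard is d/(T_e + T_f), but the literal rule uses d/T_e, which is larger whenever T_f > 0. DOR comes out shorter than under the PFS rule if d/T_e exceeds the pre-therapy hazard. With short follow-up T_f is large, so this is likely. With long follow-up T_f shrinks, and effective later therapy can reverse the direction.

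**4. Inputs for size.** The plan states no DOR or TTP figure to reproduce. The cut-off depends on the PFS event count, which does reproduce: 4 × (1.960 + 1.282)² / (ln 0.6)² = 4 × 10.51 / 0.2609 = 161.1, so 162 events.
- From the documents: uniform accrual of 15 patients per month, cut-off about 18 months after first patient in, assessments every 28 days.
- Assumed: median DOR of 6, 9 or 13 months; new therapy as the first transition in 10%, 20% or 35% of responders; median time from new therapy to event of 3 months, or 1, 2 or 4 times the DOR median. That is 3 × 3 × 4 = 36 scenarios.

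**5. Results at 18 months.**
- 12-month DOR was lower under the literal rule than under the PFS rule in all 36 scenarios, by about 0.3 to 11 percentage points.
- The median was 0 to 3.7 months shorter.
- Against ignoring new therapy, the literal rule was lower by about 0.3 to 15 points.
- Example (median 9 months, 20% switching, hazard unchanged by new therapy): PFS rule 39.5%, literal rule 36.4%, therapy ignored 39.8%. The gaps are 39.5 − 36.4 = 3.1 and 39.8 − 36.4 = 3.4 points.

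**6. A second simulation.** It used 400,000 responders, 3 to 15 months of follow-up after response and a 6-month median from new therapy to the next event (all assumed). The literal rule added about 2 to 5 events per 100 responders.

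| Switching before progression | Median DOR, PFS rule | Median DOR, literal rule | Difference (months) |
|---|---|---|---|
| 10% | 8.0 | 7.8 | 0.2 |
| 10% | 12.1 | 11.5 | 0.6 |
| 20% | 8.0 | 7.5 | 0.5 |
| 20% | 12.0 | 10.8 | 1.2 |

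**7. Longer follow-up.** With a 51-month cut-off, median DOR 6 months, 35% switching and a post-therapy median of 24 months, the literal rule gave a longer median than the PFS rule (7.4 against 6.4 months). SAP Table 10 schedules DOR only at the primary PFS analysis, so the 18-month results are the relevant ones.

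**The case against.** The strongest answer is that nobody intended a different rule. Section 2.4.4.2 introduces its TTP and DOR sentence by likening it to the primary PFS analysis, and protocol Section 11.4.2.2.2 does the same. The TTP definition and the protocol synopsis refer outright to the PFS censoring rules. The cut-off-only phrasing is the protocol's shorthand for PFS itself, which the SAP then spells out. This stands as evidence of intent. It does not remove the problem: the DOR definition contains no cross-reference, and a programmer who follows it as written would produce the mixed rule. Section 2.4.4.2 shows the safer way for high-risk PFS, where it cites the primary analysis rules without restating them.

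The objection also disposes of two stronger readings. A reader might infer that the SAP departs from the protocol. It does not: the protocol's PFS wording has the same gap, so the mismatch lies inside the SAP. A reader might also infer that primary PFS is affected, because the protocol's PFS rule is loosely worded. SAP Section 2.1.3.1 and Table 13 settle that explicitly.

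Finally, the SAP history table says that the amendment behind version 3 came after the primary analysis, and Table 10 lists no later DOR analysis. New wording would therefore mainly document the rule for results already due. That bears on the cost and leaves the text unclear.

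**Conclusion.** The point holds as a drafting gap within the SAP. The DOR definition and the TTP/DOR analysis text do not carry over the condition that makes the PFS rule coherent, and read literally they make censoring depend on the later outcome. For TTP, the definition and the analysis text agree only if the latter is read as shorthand.

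At the planned PFS cut-off the literal rule is expected to shorten DOR. The size rests on assumed DOR medians, switching rates and post-therapy times. It runs from negligible to about 11 points on 12-month DOR, or 3.7 months on the median.

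A reader might infer that the rule always shortens DOR, or that it favours one arm. Neither is supported: the direction can reverse with long follow-up, and the documents give no switching rates by arm. TTP shares the wording but was not simulated.

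DOR and TTP are descriptive and outside the testing hierarchy, so type I error, power, PFS, ORR and OS are unaffected. The text should be corrected, but no confirmatory conclusion depends on it.

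**What to change.** In SAP Section 2.1.3.2.2 (DOR) and Section 2.4.4.2 (TTP and DOR), replace the cut-off-only condition with: *Progression (and death, for DOR) counts as an event only if it occurs before initiation of further anti-myeloma treatment and before the cut-off. Otherwise the patient is censored at the last valid disease assessment before that treatment or at the cut-off, whichever is first, regardless of later events, as in Section 2.1.3.1.* Make the same change to the PFS rule in the protocol synopsis and to protocol Sections 11.4.2.1 and 11.4.2.2.2.

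The cost is a few sentences, and slightly fewer DOR and TTP events than under the literal reading. If DOR or TTP has already been produced, check which rule was programmed. The tables need re-running only if it was the literal one.

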### **Time to first response (TT1R)**

TT1R is defined as the time from randomization to the date of first IRC determined response (PR or better) that is subsequently confirmed. In the absence of response, patients will be censored at the earliest of the date of the last valid disease assessment before disease progression or death, the date of the last valid disease assessment before initiation of a further anti-myeloma treatment (if any) or the analysis cut-off date, whichever comes first.

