### **Time to best response (TTBR)**

TTBR is defined as the time from randomization to the date of first occurrence of IRC determined best overall response (PR or better) that is subsequently confirmed. In the absence of response patients will be censored at the earliest of the date of the last valid disease assessment before

disease progression or death, the date of the last valid disease assessment before initiation of a further anti-myeloma treatment (if any) or the analysis cut-off date, whichever comes first.

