#### **Time to Next Treatment**

TNT is defined as the time from randomization to the start of further anti-myeloma treatment. Patients who do not receive any further anti-myeloma treatment before the cut-off date will be censored at the date of their last FU visit or the cut-off date, whichever comes first. Patients with no FU visit will be censored at their last study treatment administration or the cut-off date whichever comes first.

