#### 2.4.4 Analyses of efficacy endpoints

All efficacy analyses will be performed in the ITT population. All analyses using the stratification factors will be performed using the stratification factor as per IRT. A sensitivity analysis of PFS will be performed using the stratification factor as per eCRF, if relevant.

Patients who received only one prior therapy will be classified in the “2 or 3 prior lines” stratum as per eCRF. In case the stratum “≥75 years old and >3 previous lines of therapy” has a small sample size (less than 20 patients), this stratum will be collapsed with the “<75 years old and >3 previous lines of therapy” stratum.

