#### **Time to next treatment**

TNT will be analyzed using Kaplan-Meier methods.

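### Kaplan-Meier for time to first and best response censors patients who can no longer respond, and time to next treatment does the same to patients who die untreated; both overstate the share having the event

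*SAP*

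**What the plan says.** **TT1R and TTBR.** Both run from randomization to a confirmed IRC response of PR or better (SAP 2.1.3.2.2). For TT1R, patients with no response "patients will be censored at the earliest of the date of the last valid disease assessment before disease progression or death", at the last valid assessment before further anti-myeloma therapy, or at cut-off. TTBR has the same rule: "In the absence of response patients will be censored at the earliest of the date of the last valid disease assessment before" those events. SAP 2.4.4.2 repeats the rule and names the estimator: "These time-to-event endpoints will be analyzed using Kaplan-Meier methods". The population comes from SAP 2.4.4: "All efficacy analyses will be performed in the ITT population". Non-responders therefore sit in the risk set until they are censored.

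**TNT.** It runs from randomization to the start of further anti-myeloma treatment (SAP 2.1.9). "Patients who do not receive any further anti-myeloma treatment before the cut-off date will be censored at the date of their last FU visit" or at cut-off, and "Patients with no FU visit will be censored at their last study treatment administration" or at cut-off. SAP 2.4.10 adds: "TNT will be analyzed using Kaplan-Meier methods". Death is not mentioned.

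**Related rules.** Best overall response (SAP 2.1.3.2.1) stops counting at progression, death, further therapy or cut-off. ORR is built on it and is reported with Clopper-Pearson intervals. For the secondary endpoints, SAP 2.4.4.2 states: "Analysis of the pre-specified secondary endpoints will be descriptive only". I found no competing-risk or cumulative-incidence method for TT1R, TTBR or TNT in either document.

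**The concern.** Kaplan-Meier treats a censored patient as someone who would go on to have the event at the same rate as those still at risk. That is reasonable for a patient still in follow-up at cut-off. It fails for a patient who has progressed, died or moved to another therapy without responding, because by the SAP's own rule that patient's response status is closed. ORR counts such a patient as a non-responder, while TT1R and TTBR treat the same patient as a responder not yet observed. The two outputs then give different answers to one question.

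For TNT the closing event is death. A patient who dies without further therapy cannot start one, yet is censored at the last follow-up visit or last dose.

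At stake is the level of descriptive curves. A reader who takes the share responding, or the share on new therapy, from them would read too high a figure.

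**Working it through.** **Direction.** Let S_r be the Kaplan-Meier curve with competing events censored, S the probability of being free of both response and competing event, and Λ_r the cause-specific cumulative hazard of response.

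- True cumulative incidence: CIF(t) = ∫ S dΛ_r
- Planned curve: 1-KM(t) = ∫ S_r dΛ_r

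S cannot exceed S_r, so 1-KM is never below the CIF, and it is above it once competing events occur before later responses. This needs no assumed rate. Back-dating censoring to the last visit before progression removes patients from the risk set earlier still.

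**Inputs for size.**
- Pd median PFS 4.0 months and hazard ratio 0.60, so IPd 6.67 months (SAP 1.3)
- Pd ORR 31% (Protocol 4.3, cited pomalidomide trial)
- Assumed, because the documents do not give them: response timing, PFS among non-responders, IPd ORR, and the share dying untreated

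The documents state no figure for these three endpoints. The sample size using the same PFS inputs reproduces: 4 × (1.960 + 1.282)² / (ln 0.60)² = 42.03 / 0.2609 = 161.1, rounded up to the plan's 162 events.

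**TT1R in Pd, constant hazards.**
- Competing hazard λ_c = ln 2 / 4 = 0.1733 per month
- Response hazard λ_r = (0.31 / 0.69) × 0.1733 = 0.0779, so that 31% eventually respond
- CIF(t) = 0.31 × [1 − exp(−0.2511 t)]; 1-KM(t) = 1 − exp(−0.0779 t)

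| Month | True CIF | 1-KM |
|---|---|---|
| 4 | 19.6% | 26.8% |
| 6 | 24.1% | 37.3% |
| 12 | 29.5% | 60.7% |

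A simulation with 28-day visits and back-dated censoring gives 27.1% against 60.5% at month 12. The constant-hazard curve passes 50% at ln 2 / 0.0779 = 8.9 months, although only 31% ever respond. Varying ORR from 20% to 40% gives a month-12 1-KM of 40.5% to 75.0% against a true 18.5% to 38.8%.

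**Early response instead.** If responses occur only in the first 4 months, the hazard that yields 31% is 0.1348, and the plateau is 1 − exp(−4 × 0.1348) = 41.7%. Simulations with responses concentrated in the first four months give 43% to 50% for a non-responder median PFS of 2 to 3 months, and about 40% for 4 months. Across these cases 1-KM is about 40% to 61% against about 30% to 31%.

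**TT1R in IPd** (ORR 50% assumed, both hazards ln 2 / 6.67 = 0.1040): 35.6% true against 46.4% at month 6, and 45.9% against 71.3% at month 12.

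**TNT in Pd.** Assume a 4-month median to next therapy or death, and a share p dying untreated. At month 12, exp(−0.1733 × 12) = 0.125, so CIF = (1 − p) × 0.875 and 1-KM = 1 − 0.125^(1−p).

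| p | True CIF | 1-KM | Excess (points) |
|---|---|---|---|
| 10% | 78.8% | 84.6% | 5.9 |
| 20% | 70.0% | 81.1% | 11.1 |
| 30% | 61.2% | 76.7% | 15.4 |

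The excess grows with follow-up: at month 24 the pairs are 88.6% and 97.6%, 78.7% and 96.4%, 68.9% and 94.6%.

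**The case against.** The strongest reply is that little depends on these curves. The endpoints are descriptive and outside the PFS, ORR, OS hierarchy (SAP 2.4.4.4). TT1R and TTBR were added in SAP version 2 as exploratory. The response share itself is estimated correctly as ORR, by arm, with exact intervals and a stratified test. All of that stands. It limits the consequence but does not repair the estimator, since a descriptive curve exists to show level and timing.

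The sizes are also open to challenge, because response timing, non-responder PFS and the untreated-death share are assumed. That stands too; they are illustrations, and only the direction is certain.

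Three stronger readings are tempting, and the documents do not support them:
- **That TNT censors progression.** It does not. Only patients with no further treatment are censored; progression normally leads to the event. Death is the only competing event, and its censoring is implied, not stated.
- **That the SAP commits to reporting response probabilities by month, or quartiles, for these endpoints.** Landmark probabilities and percentiles are specified for PFS and OS; here only the method is named.
- **That a planned comparison between arms is biased.** No test or hazard ratio is planned for TT1R, TTBR or TNT. Because the design expects PFS to differ by arm, the overstatement may differ too. That is a caution for reading plotted curves side by side, not a flaw in a planned inference.

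**Conclusion.** The point holds as an estimator error of limited consequence. For TT1R and TTBR, progression, death or further therapy without response is censored although the SAP closes response counting at those events, so 1-KM exceeds the share responding and conflicts with ORR. At a 31% Pd ORR the month-12 overstatement is roughly 10 to 30 points under the timing assumptions examined. For TNT the problem is confined to death before further therapy, and the month-12 Pd excess is about 6 to 15 points if 10% to 30% die untreated, shares the documents do not give. No primary or key secondary conclusion is affected.

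**What to change.** Replace Kaplan-Meier with Aalen-Johansen cumulative incidence by arm:
- **TT1R and TTBR:** progression, death or start of further therapy without response as competing events. Median time to response may still be described, among responders only and labelled as such.
- **TNT:** death without further therapy as the competing event, stated explicitly in SAP 2.1.9.

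The event dates are already collected, so the cost is SAP wording and minor programming. Timing differs. SAP Table 10 schedules TT1R and TTBR only at the primary PFS analysis, which preceded SAP version 3, so for them this is a small re-analysis to be labelled post hoc. TNT is scheduled again at the second interim and final OS analyses, where the change can be applied directly and where more deaths will have accrued.
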